10.2.8. Treatment Week 24 (Visit T5; 168 ±7 days)

If the patient is withdrawing early from the study at this visit, proceed to [Section 10.3.2](#) for the list of the required assessments.

If the patient is withdrawing from IMP treatment at this visit, proceed to [Section 10.2.10](#) for the list of the required assessments. The patient will be asked to continue to be followed for safety using the protocol-specified visit schedule. If the patient consents for follow-up, schedule the next protocol-specified visit.

Patients who do not provide consent to continue to return to the clinic for safety assessments after withdrawing from IMP treatment will be asked to participate in phone calls from the site at protocol-specified visits, or at a minimum at 52 weeks, to inquire about the patient's current health status and collect information on AEs (eg, recent procedures, hospitalizations, and if the patient has died, the cause of death). If the patient consents for telephone contacts, schedule the next protocol-specified visit.

Patients will undergo the following assessments and procedures at Week 24 (Visit T5):

- Concomitant and prohibited medication review (ongoing)
- Assess AEs, SAEs, and potential clinical endpoints since last visit (ongoing)
- Weight
- Vital signs
- Clinical laboratory evaluations:
 - Hematology, blood chemistry, and urinalysis
 - Basic fasting lipids (TC, calculated LDL-C, HDL-C, non-HDL-C, and TG)
 - apoB
 - HbA_{1C}

- hs-CRP
- PK sample before dose
- Conduct diet and exercise counseling
- Return of IMP; assessment and recording of IMP compliance
- IWRS contact to obtain the MED ID number for IMP
- Dispense IMP and provide dosing instructions (two 100 day supply bottles)
- Schedule next visit

10.2.9. Treatment Week 36 / Telephone Visit (Visit T6; 252 ±3 days)

Patients will undergo the following assessments via telephone at Week 36 (Visit T6):

- Concomitant medication review (ongoing)
- Assess AEs, SAEs, and potential clinical endpoints
- Diet and exercise counseling
- Assessment of study drug dosing adherence

Note: If the patient discontinues at or between study visits, please proceed to [Section 10.3.2](#) for detailed instructions.

10.2.10. Treatment Week 52/EOS (Visit T7; 365 ±7days)

Patients will undergo the following assessments and procedures at Week 52 (Visit T7), when completing an End of Study (EOS) visit, withdrawing from study (early withdrawal), or withdrawing from IMP treatment:

Patients will undergo the following assessments and procedures at Week 52 (Visit T7):

- Concomitant and prohibited medication review (ongoing)
- Assess AEs, SAEs, and potential clinical endpoints since last visit (ongoing)
- PE
- Weight
- 12-Lead ECG
- Vital signs
- Clinical laboratory evaluations:
 - Hematology, blood chemistry, and urinalysis
 - Basic fasting lipids (TC, calculated LDL C, HDL C, non-HDL C, and TG)
 - apoB
 - HbA_{1C}

- hs-CRP
- PK sample before dose
- Return of IMP; assessment and recording of IMP compliance
- Complete study status in IWRS (ie, early withdrawal or completed study).

10.3. Subject Withdrawal Criteria

10.3.1. Early Withdrawal from the Study

Patients must remain in the study until the last scheduled visit at Week 52 (Visit T7) to be considered as having completed participation in the study.

Patients who withdraw from IMP prior to Week 52 (Visit T7) for any reason will be asked to continue to be followed for safety assessments, including basic fasting lipids, at clinic visit following the protocol-specified visit schedule (see [Appendix 1](#)).

Patients who temporarily withdraw from IMP prior to Week 52 (Visit T7) for any reason may restart IMP providing that 1) the patient and the investigator are in agreement regarding this course of action, 2) the patient has been off of IMP for 4 weeks or less; and 3) IMP can be started as soon as possible. For cases where the patient has been off of IMP for more than 4 weeks, the investigator must contact the medical monitor for approval prior to restarting IMP.

Patients who refuse to continue to return to the clinic for safety assessments will be asked to participate in phone calls from the site at protocol-specified visits (see [Appendix 1](#)), or at a minimum at 52 weeks, to collect information on AEs, concomitant medications, and current health status. The patient must provide consent to be contacted by phone by site personnel for the purposes of assessing current AEs and current health status.

The patient's decision to participate in the clinical study is voluntary. Patients may refuse to continue in the study and/or withdraw from participation in this study at any time, for any reason, specified or unspecified, and without penalty or loss of benefits to which the patient is otherwise entitled.

It is the right and duty of the Investigator to interrupt the treatment of any patient whose health or well-being may be threatened by continuation in this study. Such patients should be withdrawn from the study and should not be continued under a modified regimen.

Patients who are withdrawn from the study may not re-enter. The reasons for withdrawal from this study may include:

- Patient's withdrawal of consent
- Failure to comply with the protocol
- Lost to follow-up
- Illness, condition, or procedural complication (including AEs) affecting the patient's ability to participate or requiring prohibited medication
- The Sponsor or Investigator terminates the study

- In the Investigator's judgment, it is deemed in the best interest of the patient to discontinue his/her participation in the study
- Any other reason

If a patient is lost to follow-up, every reasonable effort must be made by the clinical site personnel to contact the patient and determine the reason for discontinuation/withdrawal. The measures taken to follow-up must be documented.

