10.3.2. Procedures for Early Withdrawal

If a patient withdraws or is removed from the study for any reason, all End of Study procedures should be completed. Reason for withdrawal, date of the discontinuation, and date of the last dose of study drug should be recorded in the appropriate section of the eCRF. Additionally, the discontinuation visit date must be registered in IWRS. Study drug assigned to the withdrawn patient may not be assigned to another patient.

All effort should be made to have each patient complete all study visits on schedule according to the protocol. Accommodations for early or late visits in special circumstances will be considered by the Sponsor to prevent early withdrawal. Written notice (regardless of cause) is to be provided within 48 hours of the withdrawal to the Sponsor personnel or the Medical Monitor. At the time of discontinuation, every effort should be made to ensure all relevant procedures and evaluations scheduled for the final study visit are performed. Except in the case of a medical emergency, the procedures and assessments detailed in [Section 10.2.10](#) will be performed upon the discontinuation of the study.

Patients choosing to withdraw from the study early should be encouraged to return for all study scheduled clinic visit even if they are no longer taking IMP. Patients who withdraw from all aspects of the study will be asked to consent to clinical visits or phone calls for safety assessments, including AEs, concomitant medication, and current health status through Week 52 (Visit T7).

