11.1.6.3.1. Monitoring and Management of Elevated Liver Function Tests

If at any time after randomization a patient experiences a new ALT and/or AST $>3 \times$ ULN, the patient will undergo repeat confirmatory liver function test (LFT) assessment as soon as is reasonably possible, preferably within 3 to 7 days of the laboratory result becoming available.

Repeat LFT assessment will include: 1) measurement of ALT, AST, alkaline phosphatase, total and direct bilirubin, prothrombin time (PT)/international normalized ratio (INR), eosinophil count, CK, antihepatitis A virus (total), HBsAg (confirmation of screening measurement), HCV (confirmation of screening measurement), and anti-cytomegalovirus/immunoglobulin M; 2) history of concomitant medication use; 3) history of exposure to environmental chemical agents, including ethanol; and 4) query for related symptoms. Additionally, further testing such as liver ultrasound or magnetic resonance imaging (MRI) scanning may be warranted to rule out additional pathology depending on clinical presentation and should be discussed with the Sponsor personnel or the authorized Medical Monitor.

- If repeat LFT assessment confirms ALT and/or AST $>3 \times$ ULN, consideration should be given to withdrawing the patient and administering no further doses of study drug. At the investigator's discretion, study drug may be interrupted and the patient rechallenged with study drug after LFTs have returned to baseline levels.
- If repeat LFT assessment confirms ALT and/or AST $>5 \times$ ULN, patient should be withdrawn from IMP treatment, but will be asked to continue to be followed for safety using the protocol-specified visit schedule (see [Appendix 1](#)) or more frequently if deemed by the investigator.
- If repeat LFT assessment confirms ALT and/or AST $>3 \times$ ULN in addition to any of the following, the patient should be given no further IMP treatment, but will be asked

to continue to be followed for safety using the protocol-specified visit schedule (see [Appendix 1](#)) or more frequently if deemed by the investigator:

- TB $>2 \times$ ULN

Note: In the case of patients with Gilbert's disease, TB will be fractionated and the determination of $2 \times$ ULN will be based upon direct (conjugated) bilirubin.

- INR $>1.5 \times$ ULN (unless the patient is on stable dose of anticoagulation medication)

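### One sentence in Protocol 10.3.1 makes leaving the study the consequence of a protective interruption of treatment, contradicting the rules that keep patients who stop IMP on the visit schedule

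*Protocol*

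**What the plan says.** Protocol 10.3.1 contains three instructions that can apply to the same patient.

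- **Follow-up.** "Patients who withdraw from IMP prior to Week 52 (Visit T7) for any reason will be asked to continue to be followed", on the protocol schedule and with basic fasting lipids.
- **Restart.** "Patients who temporarily withdraw from IMP prior to Week 52 (Visit T7) for any reason may restart IMP". The conditions are that patient and investigator agree, the gap is 4 weeks or less, and dosing can resume promptly. A longer gap needs medical monitor approval.
- **Removal.** "It is the right and duty of the Investigator to interrupt the treatment of any patient whose health or well-being may be threatened", where the threat comes from continuing in the study. The next sentence reads: "Such patients should be withdrawn from the study and should not be continued under a modified regimen". The paragraph after it adds: "Patients who are withdrawn from the study may not re-enter".

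The reasons listed for study withdrawal include, separately, the investigator's judgment that "it is deemed in the best interest of the patient to discontinue his/her participation in the study". Section 10.3.2 requires End of Study procedures at withdrawal and adds: "Patients who withdraw from all aspects of the study will be asked to consent to clinical visits or phone calls for safety assessments".

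**The concern.** The trigger of the removal sentence is an action on treatment, but its consequence is an action on study participation, and that consequence is final. A site cannot both withdraw a patient with no re-entry and keep the same patient on the visit schedule with restart open.

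Three things are at stake. First, observed lipid values after stopping IMP: SAP Appendix 4 has cohorts for patients with data while off treatment (cohorts 7 and 8), so the analysis expects them. Second, clinical-endpoint follow-up: cardiovascular event rates are a listed safety endpoint (Protocol 5.2.4), and the adjudicated-event table in SAP 18.3 states no cut-off relative to last dose. Third, the chance to resume IMP for a patient whose problem resolves.

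**Working it through.** **1. The texts side by side**

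| Place | When IMP is stopped or paused |
|---|---|
| 10.3.1, removal sentence | Leave the study, no re-entry |
| 10.3.1, follow-up and restart rules | Stay on schedule with lipids; restart possible |
| 10.2.5, 10.2.7, 10.2.8 (Weeks 4, 12, 24) | Asked to stay on the visit schedule; phone calls if clinic visits are refused |
| 11.1.6.3.1 (liver tests) | "study drug may be interrupted and the patient rechallenged with study drug after LFTs have returned to baseline levels"; above 5 × ULN, stop IMP and continue follow-up |
| 11.1.6.3.2 and 11.1.6.3.3 (eGFR, hemoglobin) | Stop IMP, continue follow-up |
| 11.1.6.3.4 (CK) | Hold IMP, resumption possible; if stopped, continue follow-up |
| Appendix 1, NOTE and footnote 14 | Visits continue after IMP is stopped |

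Only the first row ends participation. Section 12.8 also summarizes withdrawal from treatment due to AEs and withdrawal from the study due to AEs separately, so the protocol treats them as different events.

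**2. Which endpoints are exposed**

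The hierarchy (SAP 7.5) has six tests. Appendix 1 does not collect apoB and hs-CRP after IMP is stopped. A patient who stays off IMP therefore exposes 6 − 2 = 4: LDL-C at Weeks 12 and 24, and non-HDL-C and TC at Week 12. A patient who would have restarted before Week 12 exposes all six.

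SAP 6.4 assigns values by collection date: Week 12 is Days 72–127 and Week 24 is Days 128–211. If no later visit takes place:

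- an exit visit before Day 72 leaves both weeks empty;
- an exit visit on Days 72–127 can supply Week 12 but leaves Week 24 empty.

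**3. Scheduled follow-up at risk to Day 365**

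| Exit day | Days remaining | After the 30-day SAE window (last dose assumed on exit day) |
|---|---|---|
| 29 | 365 − 29 = 336 | 306 |
| 85 | 365 − 85 = 280 | 250 |
| 168 | 365 − 168 = 197 | 167 |

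**4. The plan's own power figure**

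Inputs (Protocol 12.2, SAP 7.1): difference 15, SD 15, 500 versus 250, two-sided alpha 0.05.

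SE = 15 × √(1/500 + 1/250) = 1.16. Standardized difference = 15 / 1.162 = 12.91. Power exceeds 0.999, consistent with the stated figure of more than 95%.

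**5. Effect on the primary comparison**

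The documents give no rate of such interruptions, so the counts are assumptions. A missing Week 12 value in an active-arm patient off treatment is imputed from placebo patients (SAP 17.1.3, Appendix 4). The error per patient is taken as near 0 for a permanent stop, if LDL-C is then placebo-like as the SAP assumes, and at most 15 points for a patient who would have been back on IMP with full effect.

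Shift in arm mean = patients × error / 500:

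- 5 × 0 / 500 = 0
- 5 × 15 / 500 = 0.15
- 20 × 15 / 500 = 0.60

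At the upper end the difference is 15 − 0.60 = 14.4, and 14.4 / 1.162 = 12.39; power is still above 0.999.

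As a harsher test, let 15% of the active arm be treated as placebo-like: 15 × 0.85 = 12.75, and 12.75 / 1.162 = 10.97, again above 0.999. Power would fall to 95% only at a difference of about (1.960 + 1.645) × 1.162 = 4.19.

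**The case against.** The strongest reply is that the sentence is narrower than it looks. It concerns patients endangered by continuing in the study, not every safety interruption, and so sits close to the best-interest reason for study withdrawal, which is legitimate. An investigator who holds that view would not agree to a restart, so the restart rule would not apply while that view lasted. The visit sections and Appendix 1 point towards retention for any reason, so sites are not without guidance on non-laboratory AEs. Section 10.3.2 still seeks later visits or calls, and generally asks that every effort be made to complete scheduled visits.

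Much of this stands, and it limits the point. The scope is the endangered patient only, the restart conflict is conditional on agreement, and loss of follow-up is possible rather than certain.

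It does not remove the conflict. The action named is interrupting treatment, no narrower subset is defined, and the follow-up rule covers stopping IMP for any reason, safety included. In 10.3.2, the encouragement to keep attending is addressed to patients who choose to leave, which does not literally include those removed by the investigator. The request to patients leaving all aspects of the study needs consent and names AEs, medication and health status, not lipids. Neither provision reopens restart after study withdrawal.

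**Conclusion.** The contradiction is real and worth correcting, but it is a conduct and data-retention problem of modest size. Where the sentence is followed, off-treatment lipids and clinical-endpoint follow-up may be lost. On assumed counts of 5 to 20 active-arm patients (1% to 4% of 500), the arm mean shifts by 0 to 0.60 points toward placebo. The upper figure requires all 20 to be patients who would have resumed with full effect, left before Day 72 and had no later visit.

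Three stronger readings are tempting and are not supported.

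- **That the primary result or its power is threatened.** The arithmetic shows otherwise, and every randomized patient stays in the FAS.
- **That safety data simply stop.** The exit visit includes lipids, AEs that require leaving the study are followed to resolution or stabilization unless the patient is lost or dies (11.2.6), SAEs are reported to 30 days after last dose, and related SAEs beyond that (11.3). TEAE tables end at last dose plus 30 days (SAP 18.1), so after a permanent stop later AEs would not enter them anyway. The adjudicated-endpoint table is the one that may lose events.
- **That withdrawing a patient from the study for safety is wrong in itself.** The protocol provides for it as a separate step. The fault is only that this sentence makes it follow from interrupting treatment.

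**What to change.** Replace the sentence in 10.3.1 with:

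> Such patients should have IMP interrupted or stopped and should not be continued under a modified dosing regimen; they will be asked to continue scheduled visits, including lipids, AEs and clinical endpoints, unless they withdraw consent or the investigator judges that leaving the study is in their best interest. IMP may be restarted only under the restart rule above and Section 11.1.6.3.

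The clause on a modified regimen must stay, because the sentence being replaced is the protocol's only explicit ban on one. Leave the listed reasons for study withdrawal and the no-re-entry line unchanged; they then govern study withdrawal and not the stopping of IMP. When to stop or restart remains a clinical decision.

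The cost is one sentence, with no new visits or assessments and no change to the sample size. It needs a protocol amendment with IRB or IEC approval (17.3) across about 125 sites, so it is best bundled with another amendment or sent first as a site clarification.

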10.3.2. Procedures for Early Withdrawal

If a patient withdraws or is removed from the study for any reason, all End of Study procedures should be completed. Reason for withdrawal, date of the discontinuation, and date of the last dose of study drug should be recorded in the appropriate section of the eCRF. Additionally, the discontinuation visit date must be registered in IWRS. Study drug assigned to the withdrawn patient may not be assigned to another patient.

All effort should be made to have each patient complete all study visits on schedule according to the protocol. Accommodations for early or late visits in special circumstances will be considered by the Sponsor to prevent early withdrawal. Written notice (regardless of cause) is to be provided within 48 hours of the withdrawal to the Sponsor personnel or the Medical Monitor. At the time of discontinuation, every effort should be made to ensure all relevant procedures and evaluations scheduled for the final study visit are performed. Except in the case of a medical emergency, the procedures and assessments detailed in [Section 10.2.10](#) will be performed upon the discontinuation of the study.

Patients choosing to withdraw from the study early should be encouraged to return for all study scheduled clinic visit even if they are no longer taking IMP. Patients who withdraw from all aspects of the study will be asked to consent to clinical visits or phone calls for safety assessments, including AEs, concomitant medication, and current health status through Week 52 (Visit T7).

11. ASSESSMENT OF SAFETY

11.1. Safety Parameters

At all clinic visits, investigators will review all safety information including vital signs, AEs, concomitant medications, and ECG reports and will ensure that the collected data are recorded into the appropriate eCRF. Additionally, clinical laboratory samples will be collected and sent for analysis and the investigator will review the results to ensure continued patient safety while participating in the study.

11.1.1. Demographic/Medical History

Demographic data and a complete medical history will be obtained from the patient. For medical history, conditions that are relevant and/or clinically significant should be captured with at least a start date (month and year) and whether the condition is ongoing or resolved. All surgeries regardless of date should be reported.

11.1.2. Vital Signs

Vital signs will include DBP and SBP as well as heart rate.

The patient should sit quietly for 5 minutes prior to collection of vital signs. At all time points, vitals will be collected prior to blood collection. Blood pressure and heart rate will be measured using a calibrated, fully automated machine with a cuff that is appropriate to the size of the upper arm. If a fully automated machine is not available, BP may be measured manually. The same method (either automated or manual) and the same arm (right or left) must be used throughout the study. The patient should be in a seated position with feet touching the floor. Patients should be seated quietly for at least 5 minutes in a chair with their backs supported, their feet flat on the ground, and their arms bared and supported at heart level.

11.1.3. Weight, Height, and Body Mass Index

Weight will be measured on a calibrated scale while fasted and after voiding. Body weight will be measured while fasting, using consistent scales, after voiding, and without shoes and outerwear (eg, coats).

Height will be measured using standard clinic procedures.

BMI will be calculated using the formula:

$$\text{BMI (kg/m}^2\text{)} = \text{weight in kg} / (\text{height in meters})^2$$

11.1.4. Physical Examination

PEs will include an assessment of the following:

- General appearance
- Skin
- Eyes, ears, nose, and throat
- Head and neck
- Extremities
- Musculoskeletal examination
- Respiratory examination
- Cardiovascular assessment, including rhythm and presence of cardiac abnormalities
- Abdominal examination
- Neurologic examination including documentation of the presence of abnormalities in mental status and motor and sensory function
- Any additional assessments necessary to establish baseline status or evaluate symptoms or adverse experiences

Documentation of the PE findings will be included in the source documentation at the clinical site. Significant findings prior to the start of study drug will be recorded on the Medical History/Current Medical Conditions page of the eCRF. Only changes from baseline physical examination findings that meet the definition of an AE will be recorded on the AE page of the eCRF.

Note: Additional information will be collected regarding muscle-related AEs. See [Section 11.2.3](#).

11.1.5. Electrocardiogram

ECG collection will be preceded by a 10-minute rest time during which the patient will remain in the supine position. At each time point, ECGs will be collected prior to blood collection. ECGs will be assessed using machine readings and physician review.

